3. POPULATIONS OF ANALYSIS

Analysis population

Patients without a valid or adequately obtained Informed Consent Form (ICF) will be excluded from any analysis population.

The following analysis populations are defined:

- **Screened set (SCR):** all patients who signed the informed consent.
- **Randomized set (RAN):** all patients who received a randomization number, regardless of receiving trial medication and including mis-randomized patients.
- **Full analysis set (FAS):** all randomized patients who were not mis-randomized. Following the intent-to-treat (ITT) principle, patients will be analyzed according to the treatment they have been assigned to at randomization. Mis-randomized patients are those who have not qualified for randomization, have been inadvertently randomized into the study but who did not enter the treatment phase and who did not receive serelaxin. Mis-randomized patients are defined as cases where randomizations were made by the site either prematurely or inappropriately prior to confirmation of the patient's final randomization eligibility. These patients should subsequently be discontinued from the study.
- **Per Protocol set (PP):** all patients in the FAS without major protocol deviations, as defined in the Patient Validation Document (PWD).
- **Safety set (SAF):** all patients who received any amount of study treatment or standard of care treatment and who have at least one post-baseline safety assessment. Of note, the statement that a patient had no adverse events also constitutes a safety assessment. Patients will be analyzed according to treatment received.

Protocol deviation

The protocol deviation concerning the mis-randomization will be detected during the course of the study and reported by means of the specific tool developed on eCRF.

All cases of prospectively defined protocol deviations (PD) will be identified prior to clinical database lock/unblinding and entered into a dedicated data panel as part of the locked database. Certain deviations may stipulate that data collected from the subjects will be excluded from analysis population(s). All exceptional cases, problems and the final decisions on the allocation of subjects to populations will be fully defined, documented and approved by the Novartis study team before data base lock (in particular before breaking the blind where applicable) and will be fully identified and summarized in the Patient Validation Document. The major protocol deviations resulting in exclusion of subjects from an analysis population are outlined in the table below:

Table 3-1: Deviations resulting in exclusion of subjects from analysis populations

Statistical Analysis Plan

Sponsor: NOVARTIS

Protocol number: CRLX030A3301

		Deviation	Exclusion from analysis set				
Category	Description	Code(s) *	SCR	RAN	FAS	PP	SAF
Selection criteria not met	Lack of written informed consent (Inclusion criteria #1)	IC001 IC001_A1	X	X	X	X	X
	Systolic blood pressure <125 mmHg at the beginning and at the end of the screening period (Inclusion criteria #3)	IC003 IC003_M1					X
	Patient hospitalized for reasons of non-AHF event (Inclusion criteria #4)	IC004 IC004_M1 IC004_A1					X
	Lack of randomization within 16 hours from presentation to the hospital (Inclusion criteria #5)	IC005 IC005_M1					X
	Lack of intravenous furosemide of at least 40 mg (or equivalent) at any time between presentation and the start of screening for the study (Inclusion criteria #6)	IC006 IC006_M1					X
	Lack of impaired renal function defined as eGFR between presentation and randomization of ≥ 25 and ≤ 75 mL/min/1.73 m ² (Inclusion criteria #7)	IC007 IC007_M1					X
	Persistent dyspnea at rest or with minimal exertion, at screening and at the time of randomization, despite standard background therapy for acute decompensated heart failure including intravenous furosemide of at least 40 mg total (or equivalent) (Exclusion criteria #1)	EC001 EC001_M1					X
	Known significant pulmonary disease (obsolete exclusion criteria of original protocol)	EC005 EC006					X
	Patients with systolic blood pressure >180 mmHg at the end of screening or persistent heart rate >130 bpm (Exclusion criteria #3)	EC034					X
	Sepsis or active infection requiring IV anti-microbial treatment (Exclusion criteria #4)	EC003					X
Exclusion criteria	Current or planned treatment with any IV vasoactive therapies or mechanical support, with the exception of IV furosemide (or equivalent diuretic) or IV nitrates at a dose of ≤ 0.1 mg/kg/hour if the patient has a SBP >150 mmHg at the start of the screening (Exclusion criteria #5)	EC004 EC004_M1 EC004_A1 EC004_M2					X
	Significant left ventricular outflow obstruction, uncorrected, such as obstructive hypertrophic cardiomyopathy or severe aortic stenosis severe aortic regurgitation and severe mitral stenosis (Exclusion criteria #6)	EC007 EC008_M1 EC009_M1 EC010_M1					X
	Clinical evidence of acute coronary syndrome currently or within 30 days prior to enrollment. (Exclusion criteria #7)	EC011					X
	AHF due to significant arrhythmias, which include any of the following: sustained ventricular tachycardia, bradycardia with sustained ventricular rate <45 beats per minute or atrial fibrillation/flutter with sustained ventricular response of >130 beats per minute (Exclusion criteria #8)	EC012 EC013 EC014					X

	Statistical Analysis Plan
	Sponsor: NOVARTIS
	Protocol number: CRLX030A3301

Category	Description	Code(s) *	Exclusion from analysis set				
			SCR	RAN	FAS	PP	SAF
Treatment deviation	Drug infusion not administered according to a weight-range adjusted dosing regimen at the nominal dose of 30 µg/kg/day.	DRUG02 DRUG02_A3 DRUG03					X
	Study drug not injected into a 250 mL intravenous bag of 5% dextrose solution or not infused through a dedicated IV line or port, using compatible tubing, infusion filters and IV bags or not following instructions in the Pharmacy Manual.	DRUG05					X
	Investigational treatment not handled and stored properly (including temperature control).	DRUG06					X
	Expired investigational treatment	DRUG07					X
	Serelaxin infusion began later than 4 hours after start of study drug preparation.	DRUG011					X
	Serelaxin administered despite patient randomized in SOC arm	DRUG12					X
	Serelaxin administered despite patient not randomized with IRT	DRUG13		X	X	X	
	Serelaxin not administered despite patient randomized in Serelaxin arm and SBP pre-infusion ≥ 100 mmHg.	DRUG14					X X
Other	Subject does not undergo any clinical evaluations of AHF signs/symptom and subject does not report any information about the need for further IV or oral HF treatment and about the occurrence of worsening HF events through Day 5	PROC03					X
	Subject does not perform the scheduled visit at Day 5	PROC03_A1					X
	Subject not randomized but entered the treatment phase	PROC06		X	X	X	
	Subject mis-randomized (i.e. subject who has not been qualified for randomization, has been inadvertently randomized into the study, who did not enter the treatment phase and who did not undergo Serelaxin administration)	PROC07			X	X	X

* Deviations codes as defined in the Protocol Deviation Handling Document (blind & unblind). Codes could possibly change before database lock.

In addition, deviations not defined in the protocol resulting in exclusion of subjects from an analysis population are outlined in the table below.

Table 3-2: Non-protocol deviations resulting in exclusion of subjects from analysis populations

Category	Description	Non-Protocol Deviation	Exclusion from analysis set				
			SCR	RAN	FAS	PP	SAF
Non-protocol deviation	Subject has no post-baseline safety assessment.						X

	Statistical Analysis Plan
	Sponsor: NOVARTIS Protocol number: CRLX030A3301

Category	Description	Exclusion from analysis set				
		SCR	RAN	FAS	PP	SAF
Non-protocol deviation	Subject randomized to Serelaxin group but not receiving any dose of study medication				X	X

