4.1 Inclusion criteria

Subjects must fulfill **all** of the following criteria at screening to be eligible for the study. The screening period is defined as that interval that begins at the time the informed consent is signed and ends with the qualification of the subject for entry into the study (i.e. when subject has met all eligibility criteria):

1. Able to provide written informed consent before any study-specific assessment is performed. The AHF diagnostic assessments performed as per current local institution/hospital standard practice or as part of routine clinical care can be used to support patient screening even if performed before obtaining informed consent.
2. Male or female \geq 18 years of age with body weight \geq 40 Kg and \leq 160 Kg.
3. Systolic blood pressure \geq 125 mmHg at the beginning of the screening period (after ICF signature) and at the end of the screening period (prior to randomization).
4. Admitted/hospitalized for AHF. AHF is defined as including all of the following measured at any time between presentation and the end of screening:
 - a. Persistent dyspnea at rest or with minimal exertion, at screening and at the time of randomization, despite standard background therapy for acute decompensated heart failure including intravenous furosemide of at least 40 mg total (or equivalent)
 - b. Pulmonary congestion assessed through physical examination and chest X-Ray obtained during routine clinical practice at any time between presentation and the end of screening (prior to randomization)
 - c. N-terminal pro B-type natriuretic peptide (NT-proBNP) \geq 2,000 pg/mL or BNP \geq 500 pg/mL. For patients treated with valsartan/sacubitril (Entresto®), BNP is not suitable and only NT-pro-BNP should be assessed
5. Able to be randomized **within 16 hours** from presentation to the hospital [presentation starts as the earliest of (1) time of presentation at either the ER/ED, ICU/CCU or ward; or (2) time of first IV loop diuretic for treatment of the current AHF episode prior to arrival at the hospital] *(this includes outpatient clinic, ambulance, or previous hospital including emergency department).*

6. Received intravenous furosemide of at least 40 mg (or equivalent) at any time between presentation and the start of screening for the study

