4.2 Exclusion criteria

Patients fulfilling **any** of the following criteria are not eligible for inclusion in this study. No additional exclusions may be applied by the investigator, in order to ensure that the study population will be representative of all eligible patients.

1. Dyspnea primarily due to non-cardiac causes, such as acute or chronic respiratory disorders or infections (i.e., severe chronic obstructive pulmonary disease, bronchitis, pneumonia), or primary pulmonary hypertension sufficient to cause dyspnea at rest, which may interfere with the ability to interpret the primary cause of dyspnea.
2. Known history of respiratory disorders requiring the daily use of IV steroids (does not include inhaled or oral steroids) at least 2 months prior to randomization; need for intubation or the current use of IV steroids for COPD.
3. Patients with systolic blood pressure >180 mmHg at the end of screening or persistent heart rate >130 bpm
4. Temperature $>38.5^{\circ}\text{C}$ (oral or equivalent) or sepsis or active infection requiring IV anti-microbial treatment.
5. Current (within 2 hours prior to randomization) or planned (through the completion of study drug infusion) treatment with any IV vasoactive therapies, including vasodilators (including nesiritide), positive inotropic agents and vasopressors, or mechanical support (intra-aortic balloon pump, endotracheal intubation, assisted (invasive or non-invasive) ventilation, or any ventricular assist device, or ultrafiltration, hemofiltration or dialysis), with the exception of IV furosemide (or equivalent diuretic) or IV nitrates at a dose of ≤ 0.1 mg/kg/hour if the patient has a systolic BP >150 mmHg at the start of the screening.
6. Significant left ventricular outflow obstruction, uncorrected, such as obstructive hypertrophic cardiomyopathy or severe aortic stenosis (i.e., aortic valve area <1.0 cm² or mean gradient >50 mmHg on prior or current echocardiogram), severe aortic regurgitation and severe mitral stenosis.
7. Clinical evidence of acute coronary syndrome currently or within 30 days prior to enrollment. (Note that the diagnosis of acute coronary syndrome is a clinical diagnosis and that the sole presence of elevated troponin concentrations is not sufficient for a diagnosis of acute coronary syndrome, given that troponin concentrations may be significantly increased in the setting of AHF).

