2.3. STUDY POPULATION

Similarly to the RELAX-AHF study, subjects are selected among patients who have been admitted with AHF, who have normal to elevated blood pressure (SBP \geq 125 mmHg at the start and at the end of the screening period) and have impaired renal function defined as an eGFR \geq 25 and \leq 75 ml/min/1.73m² at screening (calculated using the sMDRD equation).

The study plans to randomize approximately 3,183 patients in approximately 450 study sites mainly in Europe.

Inclusion criteria

Subjects must fulfill all of the following criteria at screening to be eligible for the study. The screening period is defined as the interval that begins at the time the informed consent is signed and ends with the qualification of the subject for entry into the study (i.e., when subject has met all eligibility criteria):

1. Able to provide written informed consent before any study-specific assessment is performed. The AHF diagnosis assessments performed as per current local institution/hospital standard practice or as part of routine clinical care can be used to support patient screening even if performed before obtaining informed consent.
2. Male or female \geq 18 years of age with body weight \geq 40 Kg and \leq 160 Kg.

	Statistical Analysis Plan
	
Sponsor: NOVARTIS
 
Protocol number: CRLX030A3301

3. Systolic blood pressure \geq 125 mmHg at the beginning of the screening period (after ICF signature) and at the end of the screening period (prior to randomization).
4. Admitted/hospitalized for AHF. AHF is defined as including all of the following measured at any time between presentation and the end of screening:
 - Persistent dyspnea at rest or with minimal exertion, at screening and at the time of randomization, despite standard background therapy for acute decompensated heart failure including intravenous furosemide of at least 40 mg total (or equivalent)
 - Pulmonary congestion assessed through physical examination and chest X-Ray obtained during routine clinical practice at any time between presentation and the end of screening (prior to randomization)
 - N-terminal pro B-type natriuretic peptide (NT-proBNP) \geq 2,000 pg/mL or BNP \geq 500 pg/mL. For patients treated with valsartan/sacubitril (Entresto[®]), BNP is not suitable and only NT-pro-BNP should be assessed.

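### Two rows of SAP Table 3-1 do not state the deviation they cite: EC001 describes inclusion criterion 4a instead of exclusion criterion 1, and the SBP row says 'and' where failing the criterion means 'or'.

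*SAP*

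**What the plan says.** SAP Section 3 introduces Table 3-1 as an outline of the major protocol deviations that exclude subjects from an analysis population. Two of its eligibility rows matter here.

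- **EC001/EC001_M1.** The description starts "Persistent dyspnea at rest or with minimal exertion, at screening and at the time of randomization" and ends "including intravenous furosemide of at least 40 mg total (or equivalent) (Exclusion criteria #1". The code and the label both point to exclusion criterion 1.
- **IC003/IC003_M1.** The description is "Systolic blood pressure <125 mmHg at the beginning and at the end of the screening period (Inclusion criteria #3".

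The criteria that these rows cite read differently.

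- Protocol Section 4.2, exclusion criterion 1: "Dyspnea primarily due to non-cardiac causes, such as acute or chronic respiratory disorders or infections". SAP Section 2.3 has the same text as its first exclusion criterion.
- Protocol Section 4.1, inclusion criterion 4a: "Persistent dyspnea at rest or with minimal exertion, at screening and at the time of randomization, despite standard background therapy". This is the text that appears in the EC001 row.
- Protocol Section 4.1, inclusion criterion 3: systolic pressure of at least "125 mmHg at the beginning of the screening period (after ICF signature) and at the end of the screening period (prior to randomization".

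The PP set is the FAS without major deviations, as defined in the Patient Validation Document (SAP Section 3; Protocol Section 9.1.3). It is used to repeat the primary analysis as supportive information (SAP Section 5.2; Protocol Section 9.4.4).

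**The concern.** A deviation table should describe, row by row, how each cited criterion is failed. The EC001 row instead describes how an inclusion criterion is met. The SBP row joins the two time points with the conjunction of the criterion itself, although it describes failure of that criterion.

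What is at stake is who belongs to the PP set. If the rows were programmed as worded, the PP set would be close to empty because of EC001. If someone repaired EC001 by adding the missing negation, the check on the cause of dyspnea would drop out of the table. Patients ineligible on one SBP value would not be flagged by the SBP row. Treatment is open to patients, investigators and assessors (Protocol Section 5.4), so the rules for membership should be settled in writing before lock and not interpreted at the time of allocation.

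**Working it through.** No figure in the plan needs to be reproduced; the check compares each row with the criterion it names.

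**EC001 row**

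1. Code and label: exclusion criterion 1.
2. Content: inclusion criterion 4a, almost word for word.
3. Who meets 4a? Inclusion criterion 4 is conjunctive: "AHF is defined as including all of the following measured at any time between presentation and the end of screening". Every eligible patient therefore has the condition that the row lists as a deviation.
4. There are two possible readings:

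| Reading of the row | Who is flagged | Is exclusion criterion 1 implemented? |
|---|---|---|
| Literal | Everyone who meets 4a, so every eligible patient | No; the row does not ask about cause |
| With an implied 'Lack of', as printed in rows IC005 to IC007 | Patients who fail 4a | No; the row now duplicates part of inclusion criterion 4 |

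5. Do other rows fill the gap? IC004 covers patients hospitalized for something other than an acute heart failure event. EC005/EC006 covers known significant pulmonary disease, but its own label says that this is an obsolete criterion of the original protocol. Each overlaps with exclusion criterion 1; neither asks whether the dyspnea was primarily non-cardiac. The cover is partial.

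**SBP row**

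Inclusion criterion 3 requires start ≥125 and end ≥125 mmHg. Its negation is:

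NOT(start ≥125 AND end ≥125) = (start <125) OR (end <125).

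| Start of screening | End of screening | Fails inclusion 3? | Flagged by the row as worded? |
|---|---|---|---|
| ≥125 | ≥125 | No | No |
| ≥125 | <125 | Yes | No |
| <125 | ≥125 | Yes | No |
| <125 | <125 | Yes | Yes |

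As worded, the row catches 1 of the 3 failing patterns. This is a count of patterns, not of patients. The documents give no distribution of screening SBP among randomized patients, so the number missed is unknown. The discordant patterns are plausible: Protocol Section 5.5.5 remarks on the large fluctuation of blood pressure in these patients and stresses the value taken just before the randomization call.

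**The case against.** The strongest reply is that Table 3-1 does not finally decide who is in the PP set. The SAP defines the set through the Patient Validation Document, requires allocation decisions to be documented and approved before lock, and takes the deviation codes from the Protocol Deviation Handling Document. Neither document is available here. Each row also names its criterion number and code, and SAP Section 2.3 prints the criteria in full, so a programmer could recover the intent. This stands: the rules as programmed may be right, and the finding concerns the SAP's stated rule.

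A second reply is that the SBP row is shorthand. It sits under the heading for selection criteria not met, cites inclusion criterion 3 and echoes its phrasing, so 'and' may simply list the two measurement times. That is a fair reading and probably the intended one. The words still admit the narrower rule, and a deviation table should not depend on the reader's choice.

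A reader might also infer that the EC001 error would keep patients with non-cardiac dyspnea in the PP set while removing the others. The documents do not support that. The row never tests cause, so on a literal reading a wrongly enrolled patient with non-cardiac dyspnea who met 4a would be removed with everyone else. On the other reading, IC004 and EC005/EC006 would still catch part of that group. A nearly empty PP set would also be noticed at once, so silent bias by the literal route is unlikely.

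**Conclusion.** Both rows are wrong as written, with different degrees of certainty. The EC001 mismatch is unambiguous: code and label say exclusion criterion 1, the text is inclusion criterion 4a, and no reading of the row implements exclusion criterion 1. The SBP row is wrong on its plain wording and ambiguous at best.

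The consequence is minor. The primary analysis and all secondary and exploratory efficacy analyses use the FAS, which these rows do not touch. Only the supportive PP analysis is exposed, and only if the programs follow the table's wording. It would go too far to conclude that ineligible patients will in fact be kept in the PP set, because final allocation rests on documents that are not supplied.

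One assumption should be stated. The column marks of Table 3-1 are not reliably aligned in the text read from PDF, where the single mark for these rows prints under the safety set. I take it to belong to PP, which fits the nature of the deviations and the definition of that set.

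**What to change.** 1. Replace the EC001/EC001_M1 description with the protocol's exclusion criterion 1 (dyspnea primarily due to non-cardiac causes).
2. Reword the IC003/IC003_M1 description to SBP <125 mmHg at the beginning or at the end of the screening period.
3. If failure of inclusion criterion 4a is also meant to exclude from PP, say so in the IC004 row, so that the text now in EC001 is not simply lost.
4. Before database lock, check both rows against the Protocol Deviation Handling Document, the Patient Validation Document and the programs that derive the deviations.

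Steps 1 and 2 restate criteria already in the protocol and introduce no new eligibility rule. The cost is two table rows (three if step 3 applies) and a short check of the programs. No new data are needed, and nothing changes in the FAS analyses.

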4. VARIABLES

4.1. EFFICACY PARAMETERS

Primary efficacy parameter

Worsening of Heart Failure/all cause death through Day 5

The primary efficacy variable of the study is the time to in-hospital Worsening of Heart Failure (WHF) requiring rescue therapy or all cause death through Day 5 post randomization.

In-hospital WHF through Day 5 post randomization includes worsening signs and/or symptoms of heart failure that require an intensification of intravenous therapy for heart failure or mechanical ventilation, renal or circulatory support. Such treatment can include the institution or uptitration of IV furosemide, IV nitrates or any other IV medication for heart failure, or institution of mechanical support such as assisted (invasive or non-invasive) ventilation, ultrafiltration, haemodialysis, intra-aortic balloon pump or ventricular assist device, etc. This endpoint also includes patients who die in this 5-day period of any cause before experiencing episode(s) of WHF.

A central event adjudication committee is appointed to oversee the WHF primary endpoint adjudication.

Relevant evaluations to detect in-hospital WHF are performed in the serelaxin arm at 6, 12, 24 and 48 hours from start of study drug infusion, daily through index hospitalization, at Day 5 and discharge, and then at Day 14. For patients in the SOC arm, relevant evaluations are performed at 6, 12, 24 and 48 hours from randomization, daily through index hospitalization, at Day 5 and discharge, and then at Day 14.

Death information is collected in a dedicated eCRF section.

Secondary efficacy parameters

In-hospital Worsening of Heart Failure/all cause death/hospital readmission for HF through Day 14

The secondary efficacy endpoint is time to worsening HF requiring rescue therapy as defined above, or all cause death, or hospital readmission for heart failure through Day 14 post randomization.

	Statistical Analysis Plan
	Sponsor: NOVARTIS Protocol number: CRLX030A3301

Relevant evaluations to detect in-hospital WHF are performed in the serelaxin arm at 6, 12, 24 and 48 hours from start of study drug infusion, daily through index hospitalization, at Day 5 and discharge, and then at Day 14. For patients in the SOC arm, relevant evaluations are performed at 6, 12, 24 and 48 hours from randomization, daily through index hospitalization, at Day 5 and discharge, and then at Day 14.

Death and re-hospitalization information are collected in dedicated eCRF sections.

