Only adjudicated endpoints will be counted in the primary analysis. The “adjudicated endpoint” refers to an endpoint and date of the endpoint that has been confirmed by an independent adjudication committee who has no access to the treatment code. According to the information from the endpoint adjudication committee, the following rules will be applied to determine if an event reported in eCRF should be considered valid for the analysis or not:

Table 5.2-1: Rule for inclusion of events into the analysis

Included in the analysis	
WHF/death reported in the dedicated page of the eCRF and confirmed by adjudication committee	YES
WHF/death reported in the dedicated page of the eCRF and NOT confirmed by adjudication committee	NO

If more than one in-hospital WHF occurred, the first one will be used as the event. Censoring and time will be defined according to the following rule:

Table 5.2-2: Censoring and time rules

	Status	Time
At least one in hospital WHF and/or death occurred and:		
Difference between date and time of first occurrence of WHF/death and date and time of randomization +1 minute >120 hours	Censored	120h
Difference between date and time of first occurrence of WHF/death and date and time of randomization +1 minute \leq 120 hours	Event	Calculated difference
No in hospital WHF and death occurred and:		
Difference between date and time of last assessment* and date and time of randomization +1 minute >120 hours	Censored	120h
Difference between date and time of last assessment* and date and time of randomization +1 minute \leq 120 hours	Censored	Calculated difference

* Last assessment is the date and time of last available post-baseline physician assessment of in-hospital WHF

In case a patient is lost to follow-up, events occurring prior to the time of lost to follow-up will be counted. If no event occurred, then the patient will be censored at the time of last post-baseline in-hospital WHF assessment available.

The primary statistical hypothesis is:

	Statistical Analysis Plan
	Sponsor: NOVARTIS Protocol number: CRLX030A3301

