$H_0: \lambda_2/\lambda_1 \geq 1$, i.e., the rate of primary event of in-hospital WHF or all cause death is greater or equal in the serelaxin group relative to the standard of care group versus the one-sided alternative $H_A: \lambda_2/\lambda_1 < 1$, i.e., the rate of in-hospital WHF or all cause death is smaller in the serelaxin group relative to the standard of care group, where λ_1 and λ_2 are the hazard rates for in-hospital WHF or all cause death in the standard of care group and serelaxin group, respectively. The ratio λ_2/λ_1 is the hazard ratio of serelaxin to standard of care.

The hypothesis will be tested based on the FAS with a Gehan's generalized Wilcoxon test at a significance level of 0.025 (one-sided).

The Kaplan-Meier estimates of the survival functions for each treatment group will be plotted and Kaplan-Meier estimates for selected time points with 95% confidence intervals will be tabulated.

The hazard ratio (relative risk) and its associated two-sided 95% confidence interval will be estimated based on a Cox proportional hazards model with treatment assignment as a factor.

In addition, a description of all in-hospital WHF that occurred through Day 5 will be provided: absolute frequencies and proportions of patients with in-hospital WHF at each assessment time point will be presented overall and by concomitant medication (IV therapy with vasoactives, IV therapy with loop diuretics, oral therapy with loop diuretics, IV therapy with inotropes vasoactives) given (new, restarted or increased dose of medication), and/or by the need of mechanical/surgical intervention (yes/no) for the in-hospital WHF.

In addition to the primary analysis, the primary efficacy variable will also be analysed using the same primary analysis model on the PP set as supportive information.

Subgroup (age [65 and 75 cut off], gender, race [Caucasian and other race], region [Western Europe and Eastern Europe], ejection fractions [40% and 50% cut off], prior history of HF [naïve vs. prior history of HF]) analyses will be performed for the primary endpoint.

[figure not shown]
A Cox proportional hazards model will be fitted considering treatment as a factor and covariates the above mentioned subgroup variables. The hazard ratio (relative risk) and its associated two-sided 95% confidence interval will be estimated for treatment and factors/covariates.

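### As written, the Day 5 visit rule in SAP Table 3-1 removes patients who die before that visit from the per-protocol set, although death through Day 5 is a primary event

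*SAP*

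**What the plan says.** SAP Section 3 defines the PP set as "all patients in the FAS without major protocol deviations, as defined in the Patient Validation Document". It introduces Table 3-1 with "The major protocol deviations resulting in exclusion of subjects from an analysis population are outlined in the table below". One row, PROC03_A1, reads "Subject does not perform the scheduled visit at Day 5". The row is not limited to patients alive at Day 5, and no other section of the SAP or protocol exempts deaths.

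SAP Section 4.1 makes early death an endpoint event: "This endpoint also includes patients who die in this 5-day period of any cause before experiencing episode(s) of WHF". SAP Section 5.2 adds that "Only adjudicated endpoints will be counted in the primary analysis", places the confirmatory test on the FAS, and says that "the primary efficacy variable will also be analysed using the same primary analysis model on the PP set as supportive information". Protocol Sections 9.1.3 and 9.4.4 give the PP set the same role.

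For borderline cases, SAP Section 3 states: "All exceptional cases, problems and the final decisions on the allocation of subjects to populations will be fully defined, documented and approved". This is to happen before database lock, with the result recorded in the Patient Validation Document.

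**The concern.** A patient who dies before the Day 5 visit cannot attend it. Taken literally, the row therefore excludes such patients because they had the endpoint. It also excludes patients who had WHF and then died before the visit, so both components of the composite lose events.

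A PP analysis is meant to show whether the FAS result holds among patients treated and followed as planned. If membership depends on surviving to a visit, the analysis conditions on part of the outcome. Its agreement or disagreement with the FAS could then reflect who was removed rather than adherence. In particular, an excess of early deaths in one arm would be taken out of that arm's event count.

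**Working it through.** **Column reading.** The column marks in Table 3-1 do not survive text extraction reliably; the mark for PROC03_A1 lands in the last (Safety set) position. PP is the sound reading for three reasons.

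- The DRUG14 row has two marks squeezed into that same last position, while the comparable row of Table 3-2 marks PP and Safety separately.
- The Safety set definition in SAP Section 3 does not depend on a Day 5 visit.
- A Safety reading would also drop SOC patients who were given serelaxin (DRUG12). That set is analysed by actual treatment, and SAP Section 5.1 plans a Safety-set listing of patients whose actual and randomized treatments differ.

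**Inputs from the documents.** Planned N is 3,183 (SAP 2.3), randomized 2:1 (SAP 2.2), so 2,122 serelaxin and 1,061 SOC. The earlier phase III trial had WHF or death through Day 5 in 6.5% (serelaxin) and 12.0% (placebo) (Protocol 1.1). Those rates give an odds ratio of (0.065/0.935)/(0.12/0.88) = 0.51, as stated there. The plan attaches no figure to this rule, and the sample-size assumptions are redacted.

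**Assumptions.** Let d be the risk of dying before the visit, with or without earlier WHF, and w the risk of WHF in patients who do not die before it. All these deaths are taken as confirmed by adjudication. Every value of d, and every value of w not derived from the earlier trial, is assumed.

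**Patients removed.** 3,183 × d gives:

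- d = 0.5%: 15.9
- d = 1%: 31.8
- d = 2%: 63.7

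With composite rates of 6.5% and 12.0%, total events are 2,122 × 0.065 + 1,061 × 0.12 = 265.3. The share of events removed is then 6%, 12% or 24%.

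**Shift in the estimate.** In each arm the FAS risk is d + w and the PP risk is w/(1 − d). Ratios are serelaxin over SOC.

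| d, serelaxin / SOC | w, serelaxin / SOC | FAS ratio | PP ratio |
|---|---|---|---|
| 0.5% / 0.5% | 5% / 6% | 0.055/0.065 = 0.846 | 0.833 |
| 1% / 1% | 5% / 6% | 0.06/0.07 = 0.857 | (0.05/0.99)/(0.06/0.99) = 0.833 |
| 1% / 1% | 5.5% / 11% | 0.065/0.12 = 0.542 | 0.500 |
| 1.5% / 1% | 5% / 6% | 0.065/0.07 = 0.929 | (0.05/0.985)/(0.06/0.99) = 0.838 |
| 1% / 1.5% | 5% / 6% | 0.06/0.075 = 0.800 | (0.05/0.99)/(0.06/0.985) = 0.829 |
| 2% / 1% | 6% / 7% | 0.08/0.08 = 1.000 | (0.06/0.98)/(0.07/0.99) = 0.866 |
| 1% / 2% | 7% / 6% | 0.08/0.08 = 1.000 | (0.07/0.99)/(0.06/0.98) = 1.155 |

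These are ratios of simple proportions, used to show direction and size. They do not reproduce the Gehan test or the Cox model.

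**Is the rule needed for missing follow-up?** No. SAP Section 5.2 and Table 5.2-2 already censor event-free patients at their last physician assessment of WHF, or at 120 hours if earlier. A patient who has already had an event needs no Day 5 visit for a time-to-first-event analysis.

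**The case against.** The strongest reply is that Table 3-1 only outlines the rules. Its footnote says the codes are defined in a separate deviation-handling document and may change, and final allocation is left to the Patient Validation Document. Either may already exempt deaths. It is also natural to say that a patient who has died has not deviated from the protocol. This stands as a limit: one cannot say that deaths will be dropped, only that the SAP text drops them. It does not remove the point, because early death is foreseeable here and not an exceptional case. The SAP writes such qualifiers elsewhere: DRUG14 is restricted by pre-infusion blood pressure, and Section 5.1 has a diuretic-dose rule for patients who die before Day 5.

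The column reading is inferred. Some rows, such as DRUG13 and PROC06, appear with marks under the expected columns, so the displacement is not uniform. The PDF should settle this.

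A reader might infer that PROC03 does the same damage. The documents do not support that. PROC03 requires both that no signs-and-symptoms evaluation took place and that nothing was reported on further heart failure treatment or WHF through Day 5. Evaluations are scheduled at baseline and from 6 hours, so at most it reaches a very early death with nothing recorded.

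A reader might also infer a large bias, or one that favours serelaxin. With equal death rates the shift is small, and with unequal rates its direction depends on which arm has more deaths. The documents give no early death rates.

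**Conclusion.** The point holds for the SAP as worded: PROC03_A1, read as a PP exclusion, removes patients who die before the Day 5 visit from an analysis whose endpoint includes death. A patient who completes the visit and then dies within 120 hours is kept.

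The size is unknown. The removal of 16 to 64 patients rests on assumed death rates of 0.5% to 2% and on all the deaths counting as primary events. At 5% against 6% WHF, balanced deaths of 1% move the risk ratio by about 0.02. In the unbalanced examples the change runs from 0.03 to about 0.15, upward or downward.

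It would be wrong to conclude that the primary result is at risk. The confirmatory FAS test, its significance level and the FAS estimate do not depend on PP membership. The matter is worth correcting because the PP rerun cannot properly support the primary result if it may omit part of the endpoint.

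**What to change.** Preferred: delete PROC03_A1 as a PP exclusion and let the existing censoring at the last WHF assessment handle missed visits. Deaths removed by this rule then fall to zero, and missed visits can still be reported as deviations.

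Minimum: state in Table 3-1 that death before the scheduled visit is not a visit deviation.

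It would be a mistake to exempt patients with non-fatal WHF who miss the visit while still excluding event-free patients who miss it. PP membership would again depend on the outcome, and in an open-label trial missed visits may differ between arms.

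The cost is one line in Table 3-1, matching wording in the deviation-handling and Patient Validation documents if they repeat the rule, and a check of the column mark on the PDF. No new data are needed. The change should be made before database lock.
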